**Table 7 Sample sizes for PD differences between smokers and non-smokers and standard deviations based on the literature**

SD \ difference (mm)	0.2	0.25	0.3	0.35
	0.4	64	42	29
0.45	81	52	37	27
0.5	100	64	45	33

Abbreviation: SD = Standard deviation

Thus, the sample size selected above gives sufficient power for testing PD.

With alpha of 2.5%, power of 80%, SD of 0.5, and effect difference of 0.25 mm, then sample size needed in each arm is 64 patients. By considering 25% of drop out and product switching, 86 patients per arm, i.e., 172 patients in total, are needed.

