5.2 Product Use

The number of Cigarettes, Heatsticks, and other nicotine/tobacco containing product used daily, as reported by the patient and collected in the electronic diary, will be used to monitor product use and evaluate adherence to product allocation.

Patients will be classified according to their monthly actual product use pattern into four categories: cigarette users; IQOS user, dual user, or other as described in Figure 2. “Other” will include the following products: Other heat not burn products, e-cigarettes, Smokeless Tobacco Pipe, Smokeless Tobacco, Cigars/Pipes/Kiseru/Shisha, and Nicotine Replacement Therapy.

The calculation of the monthly product use to classify patients into the four categories is described in section 5.2.3

Confidentiality Statement

Data and information contained in this document are considered to constitute trade secrets and confidential commercial information, and the legal protections provided to such trade secrets and confidential information are hereby claimed under the provisions of applicable law. No part of this document may be publicly disclosed without the written consent of Philip Morris Products S.A

[figure not shown]

Figure 2: Product Use Categories

Abbreviations: HS, Marlboro HeatSticks; cig, cigarette

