5.2.3 Monthly product consumption

Number of monthly product (HeatSticks, cigarette, other heat not burn products, e-cigarettes, smokeless tobacco pipe, smokeless tobacco, cigars/pipes/kiseru/shisha and nicotine replacement therapy) usage will be defined the daily average (see 5.2.2) multiplied by 30.

$$\left[\text{Monthly product consumption} = 30 * \frac{\text{Total product consumption}}{\text{Total number of days}} \right]$$

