6 SAMPLE SIZE JUSTIFICATION

The sample size needed to attain 80% power to show at least a 0.25 mm gain of PD in IQOS user compared to the cigarette user categories as defined in Figure 2, using a one-sided test with 2.5% type I error probability, assuming a dropout rate of 15% and a 10% rate of patients not-adherent to product allocation was 172 patients in total (86 randomized in each arm).

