9.5.1.1 Primary Analyses

Primary Analysis of Change from Baseline in PD at V4	
Population	
 • As Exposed Set For this analysis, subjects categorized in IQOS user, cigarette user or dual user will be included with initial PD \geq 4mm will be included.
	The primary analysis will be performed on the As Exposed Set using a mixed model for repeated measurements (MMRM). Estimates of difference in PD will be calculated for Cigarette User against IQOS User categories and Cigarette User against Dual User categories. The model will include the PD change from baseline as the dependent variable, adjusting for the following covariates; 
 1. Daily cigarette consumption at V1 2. Disease severity at V1 3. Full mouth PD at V1 4. Visit 5. Product use pattern (IQOS user, cigarette smoker or dual user) 6. Interaction between visit and product use

Confidentiality Statement

Data and information contained in this document are considered to constitute trade secrets and confidential commercial information, and the legal protections provided to such trade secrets and confidential information are hereby claimed under the provisions of applicable law. No part of this document may be publicly disclosed without the written consent of Philip Morris Products S.A

Primary Analysis of Change from Baseline in PD at V4

7. Average daily cigarette use at each visit
8. Interaction between Daily cigarette consumption at V1 and product use
9. Interaction between Disease severity at V1 and product use
10. Time since last SRP
11. Number of target tooth/teeth extracted
12. Number of non-measured target tooth/teeth extracted
13. Baseline tooth mobility

Site will be included as a random effect. The degrees of freedom will be adjusted by using Kenward Roger (KR) method. A Toeplitz structure (“type=toep”) will be specified as the covariance matrix. However, other covariance structures may be used in case of non-convergence. Covariates 8-12 will be assessed for adequacy in the model using a step-wise (backward) approach through the following algorithm.

1. Fit a full model using maximum likelihood with all covariates
2. Perform a likelihood ratio test for the full model and drop the covariate with the largest p-value for the likelihood ratio statistic if it is more than 0.05.
3. Drop one covariate (only covariates 7-14) and re-fit the model.

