4. Perform a likelihood ratio test and drop the covariate with the largest p-value for the likelihood ratio statistic if it is more than 0.05.
5. Repeat steps 2 and 3 until no more covariates can be dropped.
6. Refit the final model with the covariates remaining in the model and estimate PD for each product use group using the restricted likelihood method.

Note that other covariates may be added if deemed necessary.

Number of subjects included in analysis, regression coefficients, 95% CI for regression coefficient, p-value for regression coefficient, Least Squares (LS) means (Cigarette User, IQOS User and Dual-User categories), Difference in LS Means (Cigarette User vs IQOS User/Dual-User) and 95% CI for Difference in LS Means will be presented.

The model fit will be assessed by the analysis of the residual (diagnostics) and by comparing the values predicted vs. the observed values (calibration).

Confidentiality Statement

Data and information contained in this document are considered to constitute trade secrets and confidential commercial information, and the legal protections provided to such trade secrets and confidential information are hereby claimed under the provisions of applicable law. No part of this document may be publicly disclosed without the written consent of Philip Morris Products S.A

Primary Analysis of Change from Baseline in PD at V4	
	The residuals, predicted vs observed values from the final model will be plotted.
Target visit	: V4 (6 Months)
Sample code	
ODS GRAPHICS ON;
 
PROC MIXED DATA = X METHOD=ML (REML for final model);
 
CLASS Product_use Subject Visit site;
 
MODEL PD reduction (Dependent variable) = avisit avisit*trt01a 3 4 5 6 7 8 9 10 11 12/ ddfm=kr outp=dsn residuals vciry;
 
RANDOM Site;
 
REPEATED / subject=visit (subject) type=toep;
 
LSMEANS Product_use * Visit / CL ALPHA=0.025 DIFF E UPPER;
 
RUN;
 
Where 1 2 3 4 5 6 7 8 9 10 11 12 refers to the covariates.
 
ODS GRAPHICS OFF;

Output	
15.4.5.1 Primary Analysis of Change from Baseline in Pocket Depth (mm) at V4 with Initial Pocket Depth \geq 4 mm - As Exposed Set -
 
15.4.5.2 Regression Coefficients and Graphical Diagnostics of Primary Analysis of Change from Baseline in Pocket Depth (mm) at V4 - As Exposed Set -
 
15.4.5.3 Primary Analysis of Change from Baseline in Pocket Depth (mm) at V4: Variables Dropped - As Exposed Set -

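### The primary PD model adjusts the user-category contrast for cigarettes smoked after randomisation, a count from the same diary totals that define the categories, and the SAP makes the term both fixed and removable

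*SAP*

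**What the plan says.** SAP 9.5.1.1 models PD change from baseline with 13 numbered covariates. Item 5 is product use pattern, item 6 is its interaction with visit, and item 7 is "Average daily cigarette use at each visit". SAP 5.2.5 defines item 7 as total cigarettes from randomisation to V3 or V4, divided by the days elapsed.

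The categories come from the same source. SAP 5.2 states: "The calculation of the monthly product use to classify patients into the four categories is described in section 5.2.3". In 5.2.3, monthly "usage will be defined the daily average (see 5.2.2) multiplied by 30", and 5.2.1 takes the totals from the post-randomisation questionnaires.

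On selection, the lead-in reads "Covariates 8-12 will be assessed for adequacy in the model using a step-wise (backward) approach through the following algorithm", which leaves item 7 fixed. Step 3 reads "Drop one covariate (only covariates 7-14) and re-fit the model", which makes it removable and runs past the end of the list. The note to the sample code numbers the covariates "1 2 3 4 5 6 7 8 9 10 11 12", one short of the list.

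Protocol 12.6 adjusts for V1 cigarette consumption, V1 severity, V1 full-mouth PD, exposure group and its interaction with visit. It has no on-study cigarette count. SAP section 7 declares only the change to the As Exposed Set and the removal of the Adherent Use Set.

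The planned difference in SAP section 6 is a "0.25 mm gain of PD in IQOS user compared to the cigarette user categories as defined in Figure 2". Protocol 12.2 gives the planning values (SD 0.5, one-sided 2.5%, 80% power) and concludes that the "sample size needed in each arm is 64 patients".

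**The concern.** The planned comparison is already between actual-use categories, so the objection is not simply that item 7 is measured after randomisation. It is that the V4 value of item 7 is, apart from the cut-off date, the classifying cigarette figure divided by 30. The model compares IQOS users with cigarette users while holding constant the quantity that helps to separate them.

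If the term is fixed, any benefit that acts through smoking fewer cigarettes is partly or wholly adjusted away. That route is plausible on the protocol's own background, since section 2.1 cites a dose-response between smoking intensity and periodontitis risk. The overlap also inflates the variance of the contrast. If the term is removable, a p-value chooses between two different contrasts. Two statisticians following this SAP could report different primary results.

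The term spreads. PD at V3 and CAL reuse the model (9.5.2.1), and the FAS and PP analyses refer back to it (9.5.1.2, 9.5.2.2). The biomarker-of-exposure models carry it as item 8 with no selection step, although protocol 12.7 does not list it.

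**Working it through.** **1. The plan's own figure.** n per group = 2 × 0.5² × (1.96 + 0.842)² / 0.25² = 62.8, so 63 by the normal approximation. The noncentral t gives 64 (power 80.1%). Then 64 / 0.75 = 85.3, so 86 per arm and 172 in total. The stated size reproduces, and it is for the difference between user categories without item 7.

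**2. Variance inflation from item 7.** With two equal groups, VIF = 1/(1 − R²) and R² = B/(B + W). B is the squared difference in mean cigarettes/day divided by 4, and W is the mean within-group variance.

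The base case is assumed: IQOS users uniform on 0 to 0.95/day (mean 0.475, SD 0.27), cigarette users mean 15, SD 5, no dual users.

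- B = 14.525² / 4 = 52.7 and W = (25 + 0.075)/2 = 12.5, so R² = 0.81 and VIF = 5.2 by hand.
- Simulation at 64 per group, with cigarette users kept at 1/day or more, gives 5.5.
- The SE rises from 0.5 × √(2/64) = 0.088 to 0.088 × √5.5 = 0.207.
- 0.25/0.207 − 1.96 = −0.75, which is power of about 0.23; the simulation gives 0.224.

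**3. Simulated base case.** V4 only, least squares, a likelihood-ratio test at 0.05 on this term alone, 15,000 trials per row. Entries are rejection rates, with mean estimates in mm.

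| True effect | Without item 7 | Fixed | Removable |
|---|---|---|---|
| 0.25 mm, direct | 0.803 | 0.224 (0.25) | 0.789 (0.25) |
| 0.25 mm through cigarettes, saturating as x/(x+3) | 0.805 | 0.143 (0.18) | 0.759 (0.23) |
| 0.25 mm through cigarettes, linear | 0.798 | 0.023 (0.00) | 0.575 (0.12) |
| None | 0.026 | 0.026 | 0.038 |

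**4. Sensitivity.** Cigarette-user means of 10 to 20, SD 3 to 8, and 0 or 15 dual users give 48 settings.

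- Fixed: VIF 2.0 to 23. Power with a direct effect 0.08 to 0.54.
- Removable: type I error 0.028 to 0.047 (Monte Carlo SE about 0.0035). Power 0.77 to 0.80 (direct), 0.57 to 0.79 (saturating), 0.15 to 0.73 (linear).

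These ranges are not bounds. A separate hand calculation with IQOS users at mean 0.3, SD 0.3 and cigarette users at means 12 to 18, SD 4 to 8 gave VIF 2.1 to 10.7 and fixed, direct power 0.14 to 0.50.

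**5. Closer to the SAP model.** This version used V3 and V4 together, category by visit, the baseline consumption stratum, and an assumed within-patient correlation of 0.6. VIF was 5.2. Fixed power was 0.238, 0.139 and 0.026 (direct, saturating, linear). Removable power was 0.787, 0.744 and 0.560, with type I error 0.039. Site and competing selection among the other covariates were not modelled.

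**The case against.** **The removable reading may be intended.** In the parallel GCF model (SAP 9.5.3) the same term is item 8 and both range statements say 7 to 12, so it can be dropped. That hints at a numbering slip in 9.5.1.1. Under that reading the power loss is small unless the effect is largely and linearly mediated. This stands as a hint. It does not settle the text, and the type I error still rises.

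**Protocol 12.1 leaves detail to the SAP**, and planned outputs list regression coefficients and variables dropped. So adding a covariate is not forbidden, and the choice would be visible afterwards. It would still not be fixed in advance, and this covariate changes what the contrast estimates.

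**Variance inflation as a fact.** A reader might infer that power of 0.22 is what the plan delivers. The documents do not support that. The thresholds are in a figure not shown, and every smoking distribution above is assumed.

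**Biomarkers.** A reader might infer that adjusting total NNAL and CEMA for cigarettes removes the contrast. That goes too far. The outcome is on the log scale and the covariate is not. If the marker is assumed proportional to cigarettes plus a background of 0.3 to 3 cigarette-equivalents, 38% to 66% of the log contrast survives. The supportable word is attenuates, by an amount the documents do not allow to be computed.

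**FAS and PP.** A reader might take it as settled that the arm comparison is conditioned on later smoking. SAP 9.5.1.2 says only to refer to the primary analysis, whose item 5 is use pattern, while SAP section 8 says these sets are analysed by randomised product. Conditioning follows only if the model is carried over without rewriting.

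**Conclusion.** The point holds, and three parts need no assumption. Item 7 is built from the totals that define the contrasted categories. It is absent from protocol 12.6 and undeclared in SAP section 7. Its status is contradictory, so the SAP does not say which contrast is the primary result.

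The size is conditional. Under the assumed distributions, the fixed reading gives variance inflation of about 2 to 23 (base case 5.5), and power of 0.08 to 0.54 (base case about 0.22) even for a wholly direct effect. The removable reading gives a base-case one-sided type I error of about 0.04, with power of about 0.79 (direct), 0.76 (saturating) or 0.58 (linear mediation).

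It should not be inferred that deleting the term restores 2.5% error and 80% power. SAP 9.5.1.1 would still select other covariates by p-value, including interactions with product use, and lets further covariates be added if judged necessary. None of that was modelled here.

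**What to change.** - Delete the average daily cigarette use term from the PD and CAL models, in the As Exposed, FAS and PP analyses.
- Take it out of the biomarker models too, so that they match protocol 12.7.
- Make both selection ranges and the sample code match the covariate list.
- Record the deletion in SAP 1.1, and declare in SAP section 7 the added covariates that remain and the backward selection.
- A model with on-study cigarettes may stay as a labelled sensitivity or exploratory analysis.

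The cost is SAP wording and the matching code lines. No new data are needed.

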## 6.3 Method for Assigning Patients to Study Arms

After all assessments of V1 have been completed, patients will be randomized to 1 of the 2 study arms; continued cigarette smoking or IQOS use. Patients will be informed about their study arm allocation at V2. Randomization will be done through the Interactive Web and Voice Response System (IXRS) at any time during the visit. Patients will be randomized in one of the two study arms, IQOS arm:cigarette arm in a 1:1 ratio using a stratified randomization (based on daily cigarette consumption over the month (30 days) prior to V1 (10-19 cigarettes/day vs. >19 cigarettes/day), and disease severity (< 5 mm PD vs.  $\geq$  5 mm PD) in smokers with generalized chronic periodontitis. Disease severity is based on the tooth site having the most severe condition of PD [78]. In each arm, a quota will be applied to ensure that patients with PD  $\geq$  5 mm represent at least 50% of the randomized patients. Arm assignment for patients with PD < 5 mm will be capped at n = 80, after which enrollment of patients with PD < 5 mm will be stopped. Patients with PD < 5 mm already enrolled but not randomized may be discontinued in order to ensure that randomization quota are met. Enrollment of patients with PD  $\geq$  5 mm will continue until 172 patients are randomized. At this stage, patients' enrollment will be stopped and patients already enrolled but not randomized may be discontinued. In case patients are discontinued after V1, they will be referred to their dentist/general practitioner and will receive financial compensation for the

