## 12.6 Primary Analysis

The primary analysis evaluates the change from baseline in PD, which will be calculated for each patient across all sites with a baseline PD  $\geq 4$  mm, resulting in one value per patient per endpoint for each visit (baseline, Month 3 and 6).

The primary analysis will be performed on the As Exposed Set using a mixed model for repeated measurements (MMRM) for only subjects who have used cigarettes and/or Heatsticks. The model will include the PD change from baseline as the dependent variable, adjusting for daily cigarette consumption and disease severity at V1, full mouth PD at V1, exposure group and its interaction with visit. Site will be included as a random effect. The modeling assumptions will be evaluated and the model fit will be assessed by the analysis of the residual (diagnostics) and by comparing the values predicted vs. the observed values (calibration).

Additionally, the analysis will be performed on the FAS, PP and Adherent Use populations as a supportive sensitivity analysis. Additional sub group analyses such as for “Other” product use groups may be analyzed and will be defined in the SAP.

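### The SAP lets a significance test and an unstated variable coding decide whether the single primary contrast is a common product effect or an average over strata, through two product-use by stratum interactions that the protocol model does not have

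*SAP*

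**What the plan says.** Protocol 12.6 adjusts the primary mixed model for the two stratification factors, full mouth PD at V1, and "exposure group and its interaction with visit". It contains no interaction of product with a stratification factor.

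SAP 9.5.1.1 lists 13 covariates. Item 8 is "Interaction between Daily cigarette consumption at V1 and product use" and item 9 is "Interaction between Disease severity at V1 and product use". Both are candidates for backward elimination by likelihood ratio test, with the largest p-value dropped while it exceeds 0.05. The removable range is given once as items 8–12 and once as 7–14, although the list ends at 13; items 8 and 9 fall in both ranges. The final model is refitted by REML with whatever survives, and the reported result is one "Difference in LS Means (Cigarette User vs IQOS User/Dual-User") per comparison.

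SAP 9.5.1.1 does not say how strata are weighted in that difference. In its sample code the CLASS statement names product use, subject, visit and site but neither stratification factor, the LSMEANS statement has no observed-margins option, and the MODEL statement omits items 1 and 2, which are the stratum main effects. SAP section 7 names two departures from the protocol, the As Exposed Set and the Adherent Use Set, and not these terms.

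**The concern.** With a product-use by stratum term in the model there is no single product effect. The LS-mean difference becomes an average of stratum-specific differences, and its value and standard error depend on the weights. Under this plan two things that are not fixed in advance settle what the claim-carrying test estimates: the result of a 5% test on the outcome data, and whether a programmer codes the strata as factors or as numbers.

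The weights matter most if one stratum is small. "Disease severity is based on the tooth site having the most severe condition of PD", PD is recorded in whole millimetres (Protocol 7.3.5.3), and eligibility requires teeth with PD ≥ 4 mm, so the < 5 mm stratum consists of patients whose deepest site is exactly 4 mm. It is capped at 80 and has no minimum. Giving such a stratum half the weight would raise the standard error and move the estimate.

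**Working it through.** **Inputs from the documents.** The test is set by "using a one-sided test with 2.5% type I error probability" and the target by "The sample size needed to attain 80% power to show at least a 0.25 mm gain of PD" (SAP section 6). The assumptions are "SD of 0.5, and effect difference of 0.25 mm, then sample size needed in each arm is 64 patients" (Protocol 12.2), then 25% for dropout and product switching. The < 5 mm stratum is capped at 80 of 172, or 46.5%.

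**Assumed.** Let p be the < 5 mm share. The documents give no value; 10% to 46.5% is shown.

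**The plan's own figure.** The t-test calculation for 0.25 mm and SD 0.5 gives 63.8, so 64 per arm. 64/(1 − 0.25) = 85.3, so 86 per arm and 172 in total. Power at 64 per arm is 80.1%. The stated size reproduces.

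**If the severity interaction is kept and strata are weighted equally.** The variance of the contrast rises by 1/(4p(1 − p)). Power is from the noncentral t with 124 df.

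| p | Variance factor | SE factor | Power |
|---|---|---|---|
| 46.5% | 1.005 | 1.00 | 79.9% |
| 25% | 1.333 | 1.155 | 68.1% |
| 20% | 1.562 | 1.25 | 61.2% |
| 10% | 2.778 | 1.667 | 39.1% |

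These powers are conditional on the term being in the final model. They are not the power of the planned procedure, because elimination comes first.

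**With the elimination rule applied.** This was simulated with two groups of 64, one visit, one stratum factor and its main effect in the model, 6,000 runs, and the term kept only if the likelihood ratio p-value is at most 0.05. The share-weighted mean effect is 0.25 mm throughout.

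| p | True interaction | Term kept | Power, main-effects model | Power, elimination then equal weights | Power, elimination then observed weights |
|---|---|---|---|---|---|
| 46.5% | none | 5.3% | 80.3% | 80.3% | 80.4% |
| 20% | none | 5.8% | 79.8% | 78.3% | 79.9% |
| 10% | none | 5.3% | 80.2% | 78.6% | 80.3% |
| 46.5% | 0.25 mm | 28.9% | 79.7% | 78.4% | 80.1% |
| 20% | 0.25 mm | 20.2% | 80.2% | 66.3% | 80.4% |
| 10% | 0.25 mm | 12.8% | 80.8% | 71.0% | 80.9% |

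The 0.25 mm interaction here means a larger effect in PD ≥ 5 mm. A second run at 10% gave 69.4% against 79.9%. If the larger effect is instead in PD < 5 mm, equal weighting gives about 81–83% at these three shares.

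**How the estimate moves.** Take 0.30 mm in PD ≥ 5 mm, 0.10 mm in PD < 5 mm, and p = 20%. Equal weights give 0.5 × 0.30 + 0.5 × 0.10 = 0.20 mm. Observed weights give 0.8 × 0.30 + 0.2 × 0.10 = 0.26 mm. The interaction is 0.20 mm with SE 0.5 × √(2/64)/√(0.2 × 0.8) = 0.22, so the 5% rule keeps the term in only about 15% of trials. In the other 85% or so a common effect is reported.

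**Coding.** With strata as CLASS factors, default LS means weight the two levels 50:50. Run as the sample CLASS line stands, the strata are numeric and the LS means are taken at the covariate means, close to observed shares. If the sample MODEL line is taken literally, without the stratum main effects, dropping item 9 also drops the severity main effect, so the elimination test picks up ordinary prognostic differences. In a simplified simulation with a uniform 0.25 mm product effect, p = 20% and an assumed 0.3 mm severity effect, the term is then kept in about 69% of trials. Power is about 68% with the strata in CLASS, against about 80% with observed margins.

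**Limits.** The simulations ignore dual users (a second degree of freedom for each interaction), repeated visits, site and the other covariates.

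**The case against.** The strongest reply is that both terms are removable, so under a homogeneous effect they are nearly always dropped and almost no power is lost. That is correct. A reader might infer from the conditional table that the plan gives up much of its power, with 61% or 39% in place of 80%. The documents do not support that: those figures need the interaction kept, equal weights and a 20% or 10% stratum all at once, and none of the three is established.

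The sample CLASS line also points away from equal weighting. It is the only coding evidence available, but the code is schematic and its MODEL line is incomplete, so it does not settle the matter.

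The cap and the 50% quota for PD ≥ 5 mm guard against too many shallow-pocket patients, and at the cap equal and observed weights nearly coincide. This stands, but a cap is not a minimum.

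Equal weights can be a legitimate target, since the quota and cap shape the severity mix. That also stands, provided the choice is stated.

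Finally, the protocol defers full analysis detail to the SAP, which is to be final before database lock, with the statisticians blinded to post-randomisation PD and CAL. This answers a charge of data-driven specification. It does not answer the fact that the written rule makes the estimand depend on the data, or that section 7 omits the change.

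**Conclusion.** The point holds as a defect in the definition of the primary contrast, with a conditional power cost. Items 8 and 9 are outside the protocol model and undisclosed in SAP section 7. Elimination decides whether the contrast is a common effect or a stratum average, and the weights in the second case are left to coding.

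Elimination limits the loss to about 1–2 points when the effect is homogeneous. It protects less when stratum effects truly differ, because the term is then kept more often and the weights change the answer. With a 0.25 mm interaction favouring PD ≥ 5 mm, equal weights and an assumed 10–20% share, power is about 66–71% against about 80%; at the 80-patient cap the loss is about 2 points or less. If the larger effect lies in PD < 5 mm, power rises slightly. Observed weights keep it near 80% throughout. The size therefore rests on the < 5 mm share, the direction of any interaction and the coding, none of which the documents give.

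**What to change.** Test the primary contrast in the Protocol 12.6 model: both stratification factors as main effects in the CLASS and MODEL statements, with exposure by visit as the only interaction. Report items 8 and 9 as separate effect-modification analyses with stratum-specific estimates.

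If the terms are kept, three changes are needed together: put both strata and their main effects in CLASS and MODEL, state observed-margin weights for the primary contrast, and list the interactions in SAP section 7. Adding the observed-margins option alone is not enough, because it reweights CLASS effects and the sample code leaves the strata out of CLASS.

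Apply the same to the biomarker model in SAP 9.5.2.1. Item 7 there is the consumption by product-use interaction, Protocol 12.7 does not have it, and no elimination step is stated, so it stays in by rule.

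The cost is SAP wording and a few lines of code. No data or stratum-specific result is lost.
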